**DURATION:**

Subjects will continue on study protocol for up to 12 treatment cycles (48 weeks). Subjects who do not show objective response of their KS lesions will be removed after 6 treatment cycles (24 weeks). Protocol treatment will be discontinued if a subject develops tumor progression, unacceptable toxicity or develops one of the protocol-defined reasons for treatment discontinuation.

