#### 4.2.3 Pharmacokinetics of PTC299

Blood for PK assessments should be collected immediately pre-dose; and at 1, 2, 3, 4, 5, 6, and 8 hours after the AM dose on Day 1 and again at 1, 2, 3, 4, 5, 6, and 8 hours after the AM dose on Day 28 of cycle 1. (**Note:** the Day 28/cycle 1 PK samples can be collected up to 3 days prior to Day 28). A PK sample will also be collected prior to the AM dose on Day 15 ( $\pm$  1 day) during cycle 1 and prior to the AM dose on Day 28 of cycle 2 (or Day 1 of cycle 3 if the subject's last dose of study treatment was the evening prior). Blood samples for PTC299 PK assessments will not be collected after cycle 2. The actual sample collection times should be recorded. Please see Appendix IX for detailed collection, processing, storage and shipping instructions for PK samples.

4.2.4 Assaying secreted cytokines characteristic for KS: To measure PTC299's effect on KS we will evaluate serum and plasma for levels of the cytokines (e.g., VEGF-A, VEGF-C, VEGF-D, VEGF-R1, VEGF-R2, VEGF165b, PlGF, IL-6, and IL-8) at baseline (pre-dose of study treatment on Day 1) and mid-cycle (Day 15) of cycle 1, on Day 1 of all subsequent cycles, and at the time of treatment discontinuation and 30 days post discontinuation of study therapy. Please see Appendix IV for detailed collection, processing, storage and shipping instructions for these samples. Depending on the results of these assays, other potential serum markers characteristic for KS may also be measured.

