## **7.0 CRITERIA FOR DISCONTINUATION**

- Study medication will be interrupted or permanently discontinued for treatment related toxicities as outlined in Section 5.3.3.
- Disease progression.
- Subjects who show no more than stable disease after six 4-week cycles of treatment will be permanently removed from treatment.
- Subjects who show a partial response will be treated for up to twelve 4-week cycles.
- Subjects who show a complete response will be treated for two 4-week cycles beyond confirmation of complete response.
- Subjects who become pregnant or breast-feed or who require systemic chemotherapy for the treatment of a malignancy other than KS.
- Subjects who require treatment with medications which are disallowed as outlined in Section 5.4.2.
- Subjects who are noncompliant with respect to taking drugs, keeping appointments or having tests required for the evaluation of drug safety and efficacy.
- Subjects have the right to withdraw from the study at any time for any reason.
- The Investigator has the right to remove subjects from the study for clinical reasons which he/she believes are life threatening to the subject even if such reasons do not fall into the toxicity classifications discussed above.

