## 11.2 Statistical Analysis Plan

Descriptive statistics will be used to summarize the demographic and baseline characteristics of the study population. Subjects who do not complete the required observations will be described and evaluated separately, as necessary. Reasons for study discontinuation and date of withdrawal from study will be described

The binomial proportion and its 95% confidence interval will be used to estimate the objective (complete + partial) response rate as defined in Section 8.0. With 12 patients at the maximally treated dose, the response rate can be estimated with a 95% confidence interval with width no greater than  $\pm 28.3\%$ .

The effects of PTC299 on serum and plasma VEGF, VEGFR and cytokine profiles will be evaluated by comparing the Day 28 value with the pre-treatment value, and the Day 28 value with the lowest value obtained subsequent to Day 28. These changes will be evaluated using the paired t-test, or if the data are not normally distributed, the Wilcoxon signed rank test. Comparisons between dose levels with respect to these changes will be evaluated using ANOVA or the Kruskal-Wallis test if the data are not normally distributed.

Comparisons of on-treatment values with the pre-treatment baseline value, and with the corresponding baseline value within each cycle will be performed using paired t-tests. If the distribution of the data deviates substantially from normality, the analysis will be performed on log-transformed data. Differences in change from baseline among dose levels will be analyzed by means of ANOVA (including a test for linear dose response); if a significant effect is observed, individual comparisons among dose levels will be performed with t-tests. The pattern of responses across doses will be considered in interpreting the logical validity of the results. Results will be presented in tabular and graphic form, as appropriate.

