Immunohistochemistry (IHC) will be used to determine expression of the following: VEGF, VEGFR-2, VEGFR-3, phospho-Akt, KSHV LANA, orf59, p53 and HIF-1 $\alpha$ . We will count the number of positive cells per HPF for a total of 10 fields per section and derive an index value. We will consider a 50% change from baseline in the index value for the aforementioned markers a biological response. For each measure (VEGF, VEGFR-2, VEGFR-3, phospho-Akt, KSHV LANA, orf59, p53 and HIF-1 $\alpha$ ), we will estimate the proportion of patients who demonstrate a 50% change between baseline and on treatment (between day 22 and day 28) value. The exact binomial 95% confidence interval will be derived for each measure.

To evaluate the effects of PTC299 on tumor cell proliferation, the change in immunohistochemistry of Ki67 from the pre-treatment to the post-treatment biopsy will be tested using the Wilcoxon sign test to determine if the change is less than zero, suggesting a decrease. To evaluate the drug's effects on circulating concentrations of angiogenic factors and cytokines, HIV and KSHV loads, and T-lymphocyte subsets, changes in these levels from pre-treatment to indicated sampling times will be tested by repeated-measures ANOVA, single and multivariate analysis.

For each subject, study drug administration will be described in terms of the actual doses administered and the proportion of drug actually delivered relative to the amount that should have been delivered. The total number of cycles administered; the median (range) of cycles administered; dose modifications, dose delays, and dose omissions; and reasons for deviations from planned therapy will be described by starting dose level. The type and timing of use of concomitant drugs will also be described.

AEs and laboratory abnormalities will be summarized by type and severity grade. First-cycle DLTs, adverse events leading to death or to discontinuation from treatment, and serious adverse events will be considered with special attention.

Pharmacokinetic parameters will be calculated using the actual sample collection times. Pharmacokinetic variables will be calculated from the plasma concentration data using standard compartmental and noncompartmental methods, as appropriate for the data. Variables of interest may include  $T_{max}$ ,  $C_{max}$ ,  $C_{24h}$ ,  $AUC_{0-24}$ , and  $t_{1/2}$ . Plasma concentrations and PK parameter results will be presented in tabular and graphic form by dose level and

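### The repeated-measures ANOVA for cytokines, viral loads and T-cell subsets has no time window, although on-treatment samples after cycle 6 come only from responders

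*Combined protocol and SAP*

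**What the plan says.** **Analysis.** For circulating angiogenic factors and cytokines, HIV and KSHV loads, and T-lymphocyte subsets, Section 11.2 states that changes from the pre-treatment value "will be tested by repeated-measures ANOVA, single and multivariate analysis". It does not name the sampling times, the model terms, the covariance or the treatment of missing visits. Its one sentence on subjects with incomplete observations says that they are reported and assessed apart from the others where needed.

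The same section also plans paired comparisons for VEGF, VEGFR and cytokines: Day 28 against pre-treatment, and Day 28 against the lowest later value. For these, "These changes will be evaluated using the paired t-test, or if the data are not normally distributed, the Wilcoxon signed rank test". A further paragraph plans paired t-tests of on-treatment values against baseline, with a log transform if the data are clearly non-normal. It does not say which variables it covers.

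**Sampling.** Section 4.2.4 takes cytokines on Day 1 and Day 15 of cycle 1, then "on Day 1 of all subsequent cycles, and at the time of treatment discontinuation and 30 days post discontinuation of study therapy". Sections 4.2.1.10 to 4.2.1.12 take CD4, HIV RNA and KSHV load on Day 29 and every three cycles thereafter. Section 4.3 adds a sample at treatment discontinuation.

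**Who is still on treatment.** Section 7.0 stops treatment at progression and adds: "Subjects who show no more than stable disease after six 4-week cycles of treatment will be permanently removed from treatment". The Duration paragraph of the Schema says the same. Of the others, "Subjects who show a partial response will be treated for up to twelve 4-week cycles", and "Subjects who show a complete response will be treated for two 4-week cycles beyond confirmation of complete response".

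**The concern.** The missing visits are built into the design, and they depend on outcome. After cycle 6, being sampled on treatment means having responded. A classical repeated-measures ANOVA keeps only subjects with every visit in the analysis. Applied to the full schedule, it would use only subjects treated to the end, chiefly durable partial responders, and it would discard the early visits of everyone else.

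At stake is the trial's evidence on mechanism and on viral and immune effects. If marker change is related to tumour response, an average over responders does not estimate the effect in treated subjects. For CD4 and the viral loads, the repeated-measures ANOVA is the only test that Section 11.2 names explicitly, so no clearly assigned early comparison stands beside it.

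**Working it through.** The plan gives no sample size, power or alpha for this analysis, so it has no figure to reproduce. The check counts visits and expected subjects.

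**Inputs**
- Maximum evaluable subjects (Section 11.1): 9 + 8 + 21 = 38.
- Subjects at the Stage 3 expansion dose (Section 3.3.1): 15.
- Response rates (Section 11.1): 10% null, 35% alternative. I apply one rate to all dose levels.
- Cycle length 28 days, so Day 1 of cycle k is Day 1 + 28(k − 1), ignoring dose delays.

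**Step 1: visits before and after the cycle-6 rule**

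| Marker | Scheduled points | After the end of cycle 6 (Day 168) |
|---|---|---|
| Cytokines | Days 1, 15, 29, 57, 85, 113, 141, 169, 197, 225, 253, 281, 309 (13) | 6 (Days 169 to 309) |
| CD4, HIV RNA, KSHV | Baseline, Days 29, 113, 197, 281 (5) | 2 (Days 197, 281) |

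Day 169 may coincide with a non-responder's discontinuation visit, which leaves 5 cytokine points that are clearly responder-only.

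**Step 2: expected subjects eligible to continue past cycle 6** (N × response rate, before any other loss)
- N = 38: 38 × 0.10 = 3.8; 38 × 0.35 = 13.3.
- N = 15: 15 × 0.10 = 1.5; 15 × 0.35 = 5.25. The binomial probability of two or fewer responders is 0.816 at 10% and 0.062 at 35%.

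These are expectations, not upper limits on the number of responders. The expected number of complete 12-cycle profiles is lower still, because complete responders can stop early and responders can progress or stop for toxicity. The share not eligible is 1 − 0.35 = 65% to 1 − 0.10 = 90%, whatever N is.

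**Step 3: comparison with the lowest later value**

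Take Day 29 as the Day 28 value, since no cytokine sample is scheduled on Day 28. A subject with stable disease through cycle 6 has 4 later on-treatment samples (Days 57, 85, 113, 141). A partial responder treated for 12 cycles has 10 (Days 57 to 309). Each also has a discontinuation and a 30-day sample, giving 6 against 12. A minimum over more values tends to be lower even with no drug effect, so this comparison is tied to response.

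**Step 4: illustration of bias**

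Assume a true mean change of zero and a correlation ρ between marker decrease and a normal latent response scale. Analysing responders only gives a mean change, in SD units, of −ρ × φ(z) / p, where p is the response rate and z its upper-tail cut-off. The ratio φ(z)/p is about 1.755 at p = 0.10 and 1.058 at p = 0.35.
- ρ = 0: 0.
- ρ = 0.3: −0.53 (10%) and −0.32 (35%).
- ρ = 0.5: −0.88 (10%) and −0.53 (35%).

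Simulation with 400,000 draws per setting agrees. The correlations and their direction are assumptions; the documents give neither.

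**Step 5: size of model the data could carry**

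An unstructured covariance over the 12 post-baseline on-treatment cytokine visits has 12 × 13 / 2 = 78 parameters, which is not feasible with at most 38 subjects. Over cycles 1 to 6 there are 6 such visits and 6 × 7 / 2 = 21 parameters, still many for this N.

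**The case against.** The strongest reply is that the harm needs two things the plan does not state: deletion of incomplete subjects and a window covering all 12 cycles. An analysis limited to cycles 1 to 6 would avoid the cycle-6 removal. That is right, and it makes the point conditional. It does not remove it, because the plan also does not state the safe alternative.

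Second, a reader might infer that all the marker results would rest on responders. The documents do not support that. The paired Day 28 versus pre-treatment cytokine test needs two early values per subject and is untouched by the cycle-6 rule. A subject with stable disease also supplies seven cytokine samples through Day 141, plus those at and after discontinuation. This objection stands, although the Day 28 test is named for VEGF, VEGFR and cytokines only.

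Third, a reader might infer that Section 11.2 offers three rival analyses of the same cytokine changes, from which the most favourable could be reported. That goes too far. The on-treatment paragraph does not name cytokines, and its log transform is a fallback for non-normal data. These are secondary objectives worded as descriptive, with no alpha or decision rule. What stands is that no main contrast is named and that the remedy for non-normality differs between neighbouring paragraphs.

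Fourth, a mixed model does not by itself cure loss that depends on KS response. That also stands, and it is why the window should end at cycle 6.

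**Conclusion.** The point holds in conditional form. By rule, on-treatment samples after cycle 6 come only from responders, and the named method has no window and no missing-data rule. If it were run as a complete-case analysis over all visits, expected eligibility past cycle 6 would be 3.8 to 13.3 of at most 38 subjects, and the early contrasts would be confined to that same group. The lowest-later-value comparison is affected in any case.

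This rests on the protocol's 10% and 35% response rates applied to all dose levels, and on no other loss. The size and direction of any bias cannot be derived from the documents. A reader might infer that 65% to 90% of subjects will be discarded; the plan does not say so, and that figure is one minus the assumed response rate. The primary response and DLT analyses are not affected. The change is worth making because it is cheap, but it concerns secondary objectives.

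**What to change.** In Section 11.2:

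1. Replace the repeated-measures ANOVA with a likelihood-based linear mixed model on log-transformed values, using all available visits in cycles 1 to 6. Use baseline as covariate, visit and dose level as fixed effects, and a parsimonious covariance such as a random intercept or AR(1).
2. State a rule for values below the detection limit. Appendix VI says that the KSHV limit varies with the DNA available.
3. Name the change from baseline at the end of cycle 1 as the main contrast for each marker, with the paired tests as supportive. State that the Day 29 sample serves as the Day 28 value.
4. Say whether a discontinuation sample at the end of cycle 6 enters the model. Report other discontinuation and 30-day samples separately.
5. Label all summaries after cycle 6, and the comparison with the lowest later value if it runs past cycle 6, as descriptive. Label the post-cycle-6 on-treatment summaries as responders-only.
6. State the missing-at-random assumption for losses within the window.

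The cost is SAP wording and standard software, with no added visits or samples and no change to the treatment rules. There are two downsides. Later cycles are described rather than tested. The model also relies on missing-at-random for earlier loss to progression or toxicity, and for any complete responder who stops before cycle 6. If confirmation means four weeks' persistence, a complete response seen on Day 29 could end treatment at Day 29 + 28 + 56 = 113.

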## **12.0 ETHICAL AND REGULATORY CONSIDERATIONS**

(See Model Informed Consent)

### **12.1 Informed Consent**

The principles of informed consent described in Food and Drug Administration (FDA) regulations (21 CFR Part 50) must be followed. IRB approval of the protocol and the informed consent form must be given in writing.

The AMC Operations Center must receive a copy of the letter of approval from the IRB, which specifically approves the protocol and informed consent, before subject enrollment. The IRB must also approve any significant changes to the protocol and documentation of this approval must be sent to the AMC Operations Center. Records of all study review and approval documents must be kept on file by the Investigator and are subject to FDA inspection during or after completion of the study. AEs must be reported to the IRB. The IRB should receive notification of completion of the study within 3 months of study completion and termination. The Investigator will maintain an accurate and complete record of all submissions made to the IRB, including a list of all reports and documents submitted.

### **12.2 Changes to the Protocol**

Any change or addition to this protocol requires a written protocol amendment that must be approved by CTEP and the site's local IRB before implementation. Amendments significantly affecting the safety of subjects, the scope of the investigation or the scientific quality of the study, require additional approval by the IRB/IEC/REB.

### **12.3 Women and Minorities**

This study is being conducted by the NCI-sponsored AIDS Malignancy Clinical Trials Consortium (AMC). As part of their contractual obligations, each participating site within the AMC and the AMC as a whole is required to assure that the participation of women and minority subjects reflects the percentage representation of these populations in their geographic region and, for the AMC, the United States as a whole. As such, it is expected that the representation of subjects on this trial will reflect the constitution of the respective populations.

### APPENDIX I: SCHEDULE OF EVALUATIONS

	Eligibility	Screening/ Baseline	Day 1/ (Cycle 1)	Day 15 (Cycle 1)	Day 28 (Cycle 1)	Day 29 (Day 1 of Cycle 2)	Day 57 (Day 1 of Cycle 3)	Day 85 (Day 1 of Cycle 4)	Day 113 (Day 1 of Cycle 5)	Every 28 Days Thereafter	Treatment Discont.	Post- Treatment/ Early Discont. of Therapy
Informed Consent	X											
HIV Documentation	X 											
KS Biopsy (Diagnostic)	X 											
KS Biopsy (non-indicator KS lesion; IHC)		X			X 							
KS Biopsy (non-indicator KS lesion; viral gene expression & cellular gene transcription)		X			X 							
Skin Biopsy (morphologically normal skin)		X										
Complete Medical History		X 										
Complete Review of Signs and Symptoms		X 		X 		X 	X 	X 	X 	X 		
Complete Physical Exam (vital signs [temperature, pulse, BP, respiratory rate] height, weight)		X 		X 		X 	X 	X 	X 	X 	X	X 
KS Tumor Assessment	X 					X	X	X	X	X	X	X 
Karnofsky Performance Status	X 			X 		X 	X 	X 	X 	X 	X	X 
Concomitant Medication Review		X 		X 		X 	X 	X 	X 	X 		
Review of current and prior anti-HIV therapy, prior immune based therapy, and prior anti-tumor therapy		X 		X 		X 	X 	X 	X 	X 		
KS Staging		X										
Toxicity Evaluation				X 		X 	X 	X 	X 	X 	X	X 
CBC with Differential and Platelets		X 		X 		X 	X 	X 	X 	X 	X	
INR and aPTT	X 	X 		X 		X 	X 	X 	X 	X 		

**APPENDIX I: SCHEDULE OF EVALUATIONS – cont'd**

	Eligibility	Screening/ Baseline	Day 1/ (Cycle 1)	Day 15 (Cycle 1)	Day 28 (Cycle 1)	Day 29 (Day 1 of Cycle 2)	Day 57 (Day 1 of Cycle 3)	Day 85 (Day 1 of Cycle 4)	Day 113 (Day 1 of Cycle 5)	Every 28 Days Thereafter	Treatment Discont.	Post- Treatment/ Early Discont. of Therapy
Serum chemistries: liver enzymes (AST, ALT, alkaline phosphatase), BUN, creatinine, electrolytes (sodium, potassium, chloride, bicarbonate), calcium, phosphorus, total protein, glucose, albumin, bilirubin (direct and indirect), fasting triglycerides and total cholesterol	X 	X 		X 		X 	X 	X 	X 	X 	X	
Urinalysis	X 	X 		X 		X 	X 	X 	X 	X 		
Serum HCG Pregnancy Test	X 	X 										
CD4 count		X 				X 			X 		X	
HIV-1 plasma RNA		X 				X 			X 		X	
KSHV viral load		X				X 			X 		X	
ACTH and cortisol		X				X	X	X	X	X	X	
PK Sampling			X 	X 	X 		X 					
Cytokine Assays			X 	X 		X 	X 	X 	X 	X 	X	X 
ACSR Donation (Baseline or Day 1 – optional, if patient consents)		X 										
Chest X-ray		X 										
CT Scan		X 										
Electrocardiogram		X 										

 To be done at any time prior to study entry.

 To be done within 28 days prior to study entry.

 Subjects with a positive chest X-ray or symptoms suggestive of pulmonary disease will have a chest CT performed at study entry.

 To be done within 21 days of study entry.

 For women of child bearing potential, serum beta human chorionic gonadotropin ( $\beta$ -HCG) pregnancy test to be completed within 72 hours of initiating study treatment and at any time pregnancy is suspected.

## APPENDIX I: SCHEDULE OF EVALUATIONS – *cont'd*

-  KS tumor assessments may be performed on Day 1 prior to receiving study treatment but may be performed no earlier than 14 days before initiating study treatment. Marker lesions and body areas must be photographed at baseline, then at each assessment when the response category changes.
-  To occur at Day 15 ( $\pm 2$  days) of Cycle 1, on Day 29 (Day 1 of Cycle 2) and every cycle (28 days) thereafter.
-  To occur at Day 29 (Day 1 of Cycle 2) and every three cycles thereafter.
-  To occur between Day 22 and 28 of Cycle 1. (Biopsy can occur as late as Day 29, but will need to be performed PRIOR to the first dose of study treatment in Cycle 2.)
-  To be collected immediately pre-dose; and at 1, 2, 3, 4, 5, 6 and 8 hours after the AM dose of study treatment on Day 1 of Cycle 1 and again at 1, 2, 3, 4, 5, 6 and 8 hours after the AM dose of study treatment on Day 28 of Cycle 1. **Note:** Day 28/Cycle 1 PK sampling may occur up to 3 days prior to Day 28 for scheduling purposes.
-  To be collected prior to the AM dose of study treatment on Day 15 ( $\pm 1$  day) of Cycle 1 and prior to the AM dose on Day 28 of Cycle 2 (or Day 1 of Cycle 3 if the subject's last dose of study treatment was the evening prior).
-  To be completed 30 days after discontinuation of study therapy.
-  To be collected pre-dose of study treatment on Day 1 of Cycle 1

**APPENDIX II: KARNOFSKY PERFORMANCE SCALE**

Karnofsky Performance Scale		ECOG Performance Status Scale	
Percent	Description	Grade	Description
100	Normal, no complaints, no evidence of disease.	0	Normal activity. Fully active, able to carry on all pre-disease performance without restriction.
90	Able to carry on normal activity; minor signs or symptoms of disease.		
80	Normal activity with effort; some signs or symptoms of disease.	1	Symptoms, but ambulatory. Restricted in physically strenuous activity, but ambulatory and able to carry out work of a light or sedentary nature (e.g., light housework, office work).
70	Cares for self, unable to carry on normal activity or to do active work.		
60	Requires occasional assistance, but is able to care for most of his/her needs.	2	In bed <50% of the time. Ambulatory and capable of all self-care, but unable to carry out any work activities. Up and about more than 50% of waking hours.
50	Requires considerable assistance and frequent medical care.		
40	Disabled, requires special care and assistance.	3	In bed >50% of the time. Capable of only limited self-care, confined to bed or chair more than 50% of waking hours.
30	Severely disabled, hospitalization indicated. Death not imminent.		
20	Very sick, hospitalization indicated. Death not imminent.	4	100% bedridden. Completely disabled. Cannot carry on any self-care. Totally confined to bed or chair.
10	Moribund, fatal processes progressing rapidly.		
0	Dead.	5	Dead.

